6.2 Participant Exclusion Criteria

Subjects are excluded from the study if any of the following criteria apply:

Medical and surgical history

- History of HIV with the following exceptions:
 - Patients with CD4+ T-cell (CD4+) counts \geq 350 cells/uL
- History of AIDS-defining opportunistic infection with the following exceptions:
 - Patients without opportunistic infection within the past 12 months
 - Patients on prophylactic antimicrobials unless the specific antimicrobial drug(s) has an interaction or overlapping toxicity with the proposed treatment as determined by the investigator
- History of active Hepatitis B or Hepatitis C infection at screening with the following exceptions:
 - Patients with Hepatitis B on a suppressive antiviral therapy
 - Patients with Hepatitis C who have completed curative antiviral treatment and have an undetectable viral load
- History (within 5 years) or current evidence of neoplastic disease other than the cancer under study, except cervical carcinoma in situ, superficial noninvasive bladder tumors, curatively treated Stage I-II non-melanoma skin cancer, or any other previous cancer curatively treated <5 years before the start of treatment.

Memorial Sloan Kettering Cancer Center
[name]
[name]

- Current evidence of untreated/unstable symptomatic primary CNS tumor, metastases, leptomeningeal carcinomatosis, or spinal cord compression. Exception: Patients are eligible if neurological symptoms are stable for 14 days prior to the first treatment dose and no CNS surgery or radiation has been performed for 28 days, or 14 days of SRS.
- Current evidence of CTCAE Grade >1 toxicity before the start of treatment, except for hair loss.
 - Subjects with Grade 2 neuropathy may be eligible at the investigator's discretion.
- History or current evidence of ocular abnormalities on ophthalmologic examination that would be considered a risk factor for central serous retinopathy, RVO or neovascular macular degeneration (mild and controlled age-related macular degeneration may be acceptable at the investigator's discretion)
- Current evidence of incomplete recovery from surgery or radiotherapy at screening or planned major surgery or radiotherapy during the treatment. Minor elective surgery may be acceptable at the investigator's discretion.
- History or current evidence of significant (CTCAE Grade ≥ 2) infection or wound within 2 weeks before the start of treatment.
- History or current evidence of significant cardiovascular disease within 6 months before the start of treatment. This includes, but may not be limited to: unstable angina, new-onset angina, myocardial infarction, arterial thrombosis, pulmonary embolism, CVI/TIA/stroke, pericarditis (any CTCAE grade), pericardial effusion (CTCAE Grade ≥ 2), non-malignant pleural effusion (CTCAE Grade ≥ 2), malignant pleural effusion (CTCAE Grade ≥ 3), congestive heart failure (NYHA Class II - IV) or cardiac arrhythmia requiring anti-arrhythmic therapy, except the following
 - Subjects receiving digoxin, calcium channel blockers, or beta-adrenergic blockers may be eligible at the investigator's discretion if the dose has been stable for ≥ 2 weeks before the start of treatment.
 - Subjects with sinus arrhythmia and infrequent premature ventricular contractions may be eligible at the investigator's discretion.
- History or current evidence of malabsorption syndrome, major surgical GI resection or other GI conditions that may impair absorption of mirdametinib
- Known or suspected hypersensitivity or allergy to any of the study drugs or excipients contained in the study drug formulations. In addition, allergy to other medications or other type of hypersensitivity may warrant exclusion at the investigator's discretion.
- Female subjects who are pregnant or breastfeeding.
- History or current evidence of any other medical or psychiatric condition or addictive disorder, or laboratory abnormality that, in the opinion of the investigator, may increase the risks associated with study participation, or require treatments that may interfere with the conduct of the study or the interpretation of study results.

Prior or concomitant treatments

- Prior therapy with mirdametinib or any other MEK1/2 inhibitor (e.g., selumetinib, trametinib, cobimetinib, binimetinib) at any time before the start of treatment

Memorial Sloan Kettering Cancer Center
[name]
[name]

- Prior systemic any anti-cancer therapy within five half-lives or two weeks (whichever is shorter), excluding hormonal therapy for metastatic breast cancer, before the start of treatment.
- Prior radiotherapy to the orbital region at any time before the start of treatment
- Prior radiotherapy to tumor lesion(s) that will be chosen as target lesions within 4 weeks before the start of treatment, unless the lesion(s) exhibited objective progression between the prior radiotherapy and the screening CT or MRI scan.
 - Prior palliative radiotherapy to non-target lesions may be allowed at the investigator's discretion at any time before the start of treatment.
- Prior therapy with a live vaccine(s) within 4 weeks before the start of treatment or likely to require live vaccine(s) at any time during the treatment.
 - Injectable flu vaccine (inactivated or recombinant) may be permitted at the investigator's discretion at any time before or during the treatment.
 - Covid-19 vaccination (any type) is permitted either before or during this protocol and does not preclude trial enrollment, at the discretion of the investigator.
- Prior antibiotic therapy for active infection ≤2 weeks before the start of treatment
- Prior therapy with platelet or blood transfusion for the treatment of thrombocytopenia within 2 weeks before the start of treatment.
 - Blood transfusion for the treatment of anemia within 2 weeks before the start of treatment may be acceptable at the investigator's discretion.
 - EPO for the treatment of anemia within 2 weeks before the start of treatment may be acceptable at the investigator's discretion
- Prior therapy with G-CSF or GM-CSF for the treatment of leukopenia within 2 weeks before the start of treatment
- Prior therapy with systemic or topical ophthalmic glucocorticosteroids within 2 weeks before the start of treatment (except for subjects who receive glucocorticosteroid replacement therapy at physiologic doses and / or inhaled or non-ophthalmic topical corticosteroids)

7.0 RECRUITMENT PLAN

This is an investigator initiated trial run at Memorial Sloan Kettering Cancer Center. Cancer patients at Memorial Sloan Kettering harboring the mutations listed in the inclusion criteria will be screened and recruited utilizing automated Darwin queries and through consults placed to the Early Drug Development Service.

Potential research subjects will be identified by a member of the patient's treatment team, the protocol investigator, or research team at Memorial Sloan-Kettering Cancer Center (MSKCC). If the investigator is a member of the treatment team, s/he will screen their patient's medical records for suitable research study participants and discuss the study and their potential for enrolling in the research study. Potential subjects contacted by their treating physician will be referred to the investigator/research staff of the study.

The principal investigator may also screen the medical records of patients with whom they do not have a treatment relationship for the limited purpose of identifying patients who would

Memorial Sloan Kettering Cancer Center
[name]
[name]

be eligible to enroll in the study and to record appropriate contact information in order to approach these patients regarding the possibility of enrolling in the study.

During the initial conversation between the investigator/research staff and the patient, the patient may be asked to provide certain health information that is necessary to the recruitment and enrollment process. The investigator/research staff may also review portions of their medical records at MSKCC in order to further assess eligibility. They will use the information provided by the patient and/or medical record to confirm that the patient is eligible and to contact the patient regarding study enrollment. If the patient turns out to be ineligible for the research study, the research staff will destroy all information collected on the patient during the initial conversation and medical records review, except for any information that must be maintained for screening log purposes.

In most cases, the initial contact with the prospective subject will be conducted either by the treatment team, investigator or the research staff working in consultation with the treatment team. The recruitment process outlined presents no more than minimal risk to the privacy of the patients who are screened and minimal PHI will be maintained as part of a screening log. For these reasons, we seek a (partial) limited waiver of authorization for the purposes of (1) reviewing medical records to identify potential research subjects and obtain information relevant to the enrollment process; (2) conversing with patients regarding possible enrollment; (3) handling of PHI contained within those records and provided by the potential subjects; and (4) maintaining information in a screening log of patients approached (if applicable).

7.1 Research Participant Registration

Confirm eligibility as defined in the section entitled Inclusion/Exclusion Criteria. Obtain informed consent, by following procedures defined in section entitled Informed Consent Procedures. During the registration process registering individuals will be required to complete a protocol specific Eligibility Checklist. The individual signing the Eligibility Checklist is confirming whether the participant is eligible to enroll in the study. Study staff are responsible for ensuring that all institutional requirements necessary to enroll a participant to the study have been completed. See related Clinical Research Policy and Procedure #401 (Protocol Participant Registration).

7.2 Randomization

Study treatment blinding and randomization are not applicable in this open-label study.

8.0 INFORMED CONSENT PROCEDURES

Before protocol-specified procedures are carried out, consenting professionals will explain full details of the protocol and study procedures as well as the risks involved

Memorial Sloan Kettering Cancer Center
[name]
[name]

to participants prior to their inclusion in the study. Participants/LAR will also be informed that they are free to withdraw from the study at any time. All participants/LAR must sign an IRB/PB-approved consent form indicating their consent to participate. This consent form meets the requirements of the Code of Federal Regulations and the Institutional Review Board/Privacy Board of this Center. The consent form will include the following:

1. The nature and objectives, potential risks and benefits of the intended study.
2. The length of study and the likely follow-up required.
3. Alternatives to the proposed study. (This will include available standard and investigational therapies. In addition, patients will be offered an option of supportive care for therapeutic studies.)
4. The name of the investigator(s) responsible for the protocol.
5. The right of the participant to accept or refuse study interventions/interactions and to withdraw from participation at any time.

Before any protocol-specific procedures can be carried out, the consenting professional will fully explain the aspects of patient privacy concerning research specific information. In addition to signing the IRB Informed Consent, all patients must agree to the Research Authorization component of the informed consent form. Each participant and consenting professional will sign the consent form. The participant must receive a copy of the signed informed consent form.

9.0 PRE-TREATMENT/INTERVENTION

Patients must have a screening tumor assessment by computed tomography (CT) (preferred to assess target lesions) or magnetic resonance imaging (MRI) scans of known sites of disease as clinically indicated. If the patient has had appropriate imaging scans (e.g., routine clinical management) performed within 28 days prior to Cycle 1 Day 1, then the results of those scans may be used if they are of diagnostic quality. Subsequent post-screening tumor assessments will be done following RECIST v1.1 guideline. Response will be assessed as per RECIST v1.1 by the investigator.

Prior to enrollment, tumor tissue samples with sufficient tumor cell content must be provided during the Screening Period. Patients without satisfactory archival tumor samples, or with an archival tumor sample older than 6 months, will be required (pending the safety of obtaining this additional biopsy) to consent to a tumor biopsy prior to dosing with study drug. If the biopsy is deemed unsafe, the patient may be eligible at the discretion of the principal investigator.

Each potential research patient will provide written informed consent ≤45 days prior to initiation of treatment and prior to starting any study-specific procedures. Upon signature of

Memorial Sloan Kettering Cancer Center
[name]
[name]

the ICF, patients will be assigned a unique patient number as enrollment (Screening) occurs. All screening procedures are listed in Table 3.

10.0 TREATMENT/INTERVENTION PLAN

In all arms of this study, mirdametinib is defined as investigational product (IP) and refers to 1 mg and 2 mg capsules of mirdametinib (PD-0325901). Mirdametinib will be administered by mouth twice daily at the doses specified below.

For Arm 1 of this study, fulvestrant (Faslodex) will be administered by intramuscular (IM) injection at the dose and regimen approved by the FDA for the treatment of ER-positive metastatic breast cancer (500mg on Day 1 and Day 15 of Cycle 1 and on Day 1 of all subsequent cycles).

10.1 Mirdametinib Study Treatment

- Subjects will be instructed to take mirdametinib at home and record the time of intake for both daily doses in the patient dosing diary. Missed doses will also be recorded in the dosing diary. Subjects will be instructed to **not** take their planned morning dose of mirdametinib prior to each study visit during the treatment period. Instead, the morning dose will be taken following the pre-dose PK blood draw or any other assessment scheduled to be obtained at pre-dose during the visit.
- Mirdametinib treatment will be dispensed to subjects every two Cycles during scheduled study visits as described in the SoA or at an unscheduled visit if mirdametinib treatment is damaged/lost.
- Throughout the treatment period, subjects will self-administer study treatment BID utilizing a continuous dosing schedule in 28-day Cycles.
- Subjects will be instructed to swallow capsules whole and not to open or chew them prior to swallowing.
- No capsule should be ingested if it is broken, cracked, or otherwise not intact.
- Subjects should be encouraged to take their dose approximately every 12 hours
- Subjects can take mirdametinib capsules without regard to food intake.
- Delivery of mirdametinib via nasogastric tube or gastrostomy tube is not allowed.
- If a subject misses a scheduled dose of study treatment, and it is within 6 hours of the scheduled dose, the subject should immediately administer the missed dose and resume study treatment in accordance with the normal administration schedule. If more than 6 hours has elapsed since the time of scheduled administration, the subject will **not** be instructed to administer the missed dose and to resume study treatment as prescribed.
- Subjects should not take 2 doses together to “make-up” for a missed dose.
- If a subject vomits any time after taking a dose, then they must be instructed not to take another dose to “make up” for vomiting, but rather, to resume subsequent doses as prescribed.

Memorial Sloan Kettering Cancer Center
[name]
[name]

- If a subject inadvertently takes 1 extra dose, then the subject should not take the next scheduled dose of study treatment. Only one dose should be skipped in this context.

The dose levels for mirdametinib are summarized as follows:

Dose Level -2INT	2mg PO BID, 3 weeks on/1 week off
Dose Level -2	2mg PO BID given continuously
Dose Level -1INT	3mg PO BID, 3 weeks on/1 week off
Dose Level -1	3mg PO BID given continuously
Dose Level 1	4mg PO BID given continuously
Dose Level 2	6mg PO BID given continuously
Dose Level 3	8mg PO BID given continuously

In arm 1, dose level 1 of mirdametinib will be used in the safety run-in with fulvestrant and this dose will be used as the RP2D, otherwise dose de-escalation will be carried out. In this arm if that dose is not tolerated, this will proceed to dose level -2 with fulvestrant. If dose level -2 is not tolerated, dose level -2INT will be initiated. Arm 2 will follow a dose escalation 3+3 standard design, in which dose level 1 is the initial dose of mirdametinib, with additional dose levels 2 and 3. Pending DLTs in dose levels 1-3, this arm will proceed to dose level -1 using mirdametinib as monotherapy. If dose level -1 is not tolerated, dose level -1INT will be initiated.

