At each step of the 3+3 design, the investigators will review all available safety and PK data in the current Dose Level and decide about the appropriate next step. The subjects will become evaluable for the 3+3 decisions if they complete Cycle 1 and receive at least 80% of assigned drug doses, or if they exhibit a DLT in Cycle 1.

The starting dose of mirdametinib as single agent in each Dose Level escalation will be as follows:

- Dose Level 1: **mirdametinib 4 mg BID PO**, given continuously
- Dose Level 2: **mirdametinib 6 mg BID PO**, given continuously
- Dose Level 3: **mirdametinib 8 mg BID PO**, given continuously
- The de-escalation (Dose Level -1) may evaluate **mirdametinib 3 mg BID** given continuously, and (Dose Level -1INT) may evaluate **mirdametinib 3 mg BID** given on a 3 weeks on, 1 week off schedule. These de-escalation Dose Levels will be evaluated at investigator's discretion after the higher dose of mirdametinib is not tolerated. The de-escalation Dose Levels will be started only if the benefit-risk ratio is acceptable at the investigator's opinion.

The 3+3 decisions in Part 1 of Arm 2 will be made as follows.

1. Dose Level 1 (**mirdametinib 4 mg BID PO** given continuously)
 - a. Up to 3 subjects will be treated with mirdametinib as single agent at the dose of **4 mg BID PO** given continuously.

Memorial Sloan Kettering Cancer Center
[name]
[name]

- b. If 1 of the first 3 evaluable subjects in Dose Level 1 exhibit a DLT in Cycle 1, then Dose Level 1 will be expanded (see #2 below)
- c. If 0 of the first 3 evaluable subjects in Dose Level 1 exhibit a DLT in Cycle 1, then the dose of mirdametinib as single agent will be escalated to Dose Level 2 (**6 mg BID** given continuously) (see #4 below)

2. Dose Level 1 expansion:

- a. A sufficient number of subjects will be treated with mirdametinib as single agent at the dose of **4 mg BID PO** given continuously to accrue 6 evaluable subjects.
- b. If ≤ 1 of 6 evaluable subjects in the starting Dose Level exhibit a DLT in Cycle 1, then the dose of mirdametinib as single agent will be escalated to Dose Level 2 (**6 mg BID** given continuously) (see #5 below).
- c. If ≥ 2 of the first 3 evaluable subjects or ≥ 2 of the 6 evaluable subjects in Dose Level 1 exhibit a DLT in Cycle 1, then the mirdametinib dose will be de-escalated (see #3 below).

3. Dose Level -1 (de-escalation Dose Level **3 mg BID PO** given continuously)

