- a. Up to 3 subjects will be treated with mirdametinib as a single agent at the dose of 3 mg BID PO in Dose Level -1
- b. If ≤ 1 of the first 3 evaluable subjects in Dose Level -1 exhibit a DLT in Cycle 1, then a sufficient number of subjects will be treated with **mirdametinib 3 mg BID PO** given continuously to accrue 6 evaluable subjects.
- c. If ≤ 1 of 6 evaluable subjects in Dose Level -1 exhibit a DLT in Cycle 1, then **mirdametinib 3 mg BID PO** given continuously will be declared as the recommended dose for Part 2 (RP2D).
- d. If ≥ 2 of the first 3 evaluable subjects or ≥ 2 of the 6 evaluable subjects in the de-escalation Dose Level exhibit a DLT in Cycle 1, then the Arm 2 will be further de-escalated (see #4 below).

4. Dose Level -1INT (de-escalation Dose Level **3 mg BID PO** on a 3 weeks on, 1 week off schedule)

- a. Up to 3 subjects will be treated with mirdametinib as a single agent at the dose of 3 mg BID PO intermittently in Dose Level -1INT
- b. If ≤ 1 of the first 3 evaluable subjects in Dose Level -1INT exhibit a DLT in Cycle 1, then a sufficient number of subjects will be treated with **mirdametinib 3 mg BID PO** intermittently to accrue 6 evaluable subjects.
- c. If ≤ 1 of 6 evaluable subjects in Dose Level -1INT exhibit a DLT in Cycle 1, then **mirdametinib 3 mg BID PO** intermittently will be declared as the recommended dose for Part 2 (RP2D).

- d. If ≥ 2 of the first 3 evaluable subjects or ≥ 2 of the 6 evaluable subjects in the de-escalation Dose Level exhibit a DLT in Cycle 1, then the Arm 2 will be discontinued. The reason for discontinuation of Arm 2 would be that **3 mg BID PO** intermittently is deemed to be the minimum dose required for sufficient clinical benefit from mirdametinib as single agent in the refractory advanced cancer.

5. Dose Level 2 (Dose Level escalation **6 mg BID PO** given continuously)

- a. Up to 3 subjects will be treated with mirdametinib as a single agent at the dose of **6 mg BID PO** given continuously in Dose Level 2
- b. If ≤ 1 of the first 3 evaluable subjects in Dose Level 2 exhibit a DLT in Cycle 1, then a sufficient number of subjects will be treated with mirdametinib **6 mg BID PO** given continuously to accrue 6 evaluable subjects.
- c. If ≤ 1 of 6 evaluable subjects in Dose Level 2 exhibit a DLT in Cycle 1, then the dose of mirdametinib as single agent will be escalated to Dose Level 3 (**8 mg BID** given continuously) (see #6 below).

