- d. If ≥ 2 of the first 3 evaluable subjects or ≥ 2 of the 6 evaluable subjects in Dose Level 2 exhibit a DLT in Cycle 1, then **mirdametinib 4 mg BID PO** given continuously will be declared as the recommended dose for Part 2 (RP2D).

6. Dose Level 3 (Dose Level escalation **8 mg BID PO** given continuously)

- a. Up to 3 subjects will be treated with mirdametinib as a single agent at the dose of **8 mg BID PO** in Dose Level 3
- b. If ≤ 1 of the first 3 evaluable subjects in Dose Level 3 exhibit a DLT in Cycle 1, then a sufficient number of subjects will be treated with mirdametinib **8 mg BID PO** given continuously to accrue 6 evaluable subjects.
- c. If ≤ 1 of 6 evaluable subjects in Dose Level 3 exhibit a DLT in Cycle 1, then **mirdametinib 8 mg BID PO** given continuously will be declared as the recommended dose for Part 2 (RP2D).
- d. If ≥ 2 of the first 3 evaluable subjects or ≥ 2 of the 6 evaluable subjects in Dose Level 3 exhibit a DLT in Cycle 1, then **mirdametinib 6 mg BID PO** given continuously will be declared as the recommended dose for Part 2 (RP2D).
- e. The dose of mirdametinib as single agent will not be escalated above **8 mg BID PO** given continuously.

Arm 2 – Part 2 (expansion cohorts for mirdametinib as single agent)

One or more expansion cohorts (up to 30 subjects each) will be started, either in parallel or sequentially depending on the results of Part 1. The purpose will be to evaluate the efficacy and safety of the RP2D of mirdametinib as single agent (as determined in Part 1 of Arm 2) in the subjects with advanced solid cancers (with the exception of colorectal, small bowel, biliary and ampullary cancers) harboring activating mutations in MEK1/2.

Memorial Sloan Kettering Cancer Center
[name]
[name]

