fulvestrant. If 1 of the first 3 evaluable subjects in Dose Level -2INT exhibit a DLT in Cycle 1, then a sufficient number of subjects will be treated with mirdametinib 2 mg BID PO on a 3 weeks on, 1 week off schedule, in combination with the recommended dose of fulvestrant to accrue 6 evaluable subjects. If 1 of 6 evaluable subjects in Dose Level -2INT exhibit a DLT in Cycle 1, then **mirdametinib 2 mg BID PO on a 3 weeks on, 1 week off schedule**, will be declared as the recommended dose for Part 2 (RP2D) in combination with fulvestrant. If ≥ 2 of the first 3 evaluable subjects or ≥ 2 of the 6 evaluable subjects in Dose Level -2INT exhibit a DLT in Cycle 1, then Arm 1 will be discontinued. In the case of de-escalation there will be at least 18 evaluable patients (6 from dose level 0, and 6 on two separate dose levels of de-escalation).

Arm 2

Part 1 will be conducted in three sequential Dose Level escalations according to the 3+3 design based on the incidence of dose-limiting toxicities (DLT) and the overall safety profile of the study treatments. At each step of the 3+3 design, the investigators will review all available safety and PK data in the current Dose Level and decide about the appropriate next step. The subjects will become evaluable for the 3+3 decisions if they complete Cycle 1 and receive at least 80% of assigned drug doses, or if they exhibit a DLT in Cycle 1. The starting dose of mirdametinib as single agent in each dose escalation dose level will be as follows: mirdametinib 4 mg BID PO given continuously, mirdametinib 6 mg BID PO given continuously, mirdametinib 8 mg BID PO given continuously. The de-escalation Dose Levels (Dose Level -1) may evaluate mirdametinib 3 mg BID given continuously and (Dose Level -1INT) may evaluate mirdametinib 3 mg BID given on. 3 weeks on, 1 week off schedule.

The 3+3 decisions in Part 1 of Arm 2 will be made similar to the above. Up to 3 subjects will be treated with mirdametinib as single agent at the dose of **4 mg BID PO** given continuously. If ≤ 1 of the first 3 evaluable subjects in Dose Level 1 exhibit a DLT in Cycle 1, then Dose Level 1 will be expanded. If 0 of the first 3 evaluable subjects in Dose Level 1 exhibit a DLT in Cycle 1, then the dose of mirdametinib as single agent will be escalated to Dose Levels 2 and 3 (**6 mg BID** given continuously **and 8 mg BID** given continuously) following the same rules as above. There will thus be as many as 18 evaluable patients on this arm.

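### Sections 4.2, 10.1 and 14.1 do not give one consistent set of Arm 2 dose-finding rules, and the escalation table in 14.1 fits only the Level 1 decision

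*Combined protocol and SAP*

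**What the plan says.** Arm 2 Part 1 tests mirdametinib alone at 4, 6 and 8 mg BID continuously (Levels 1, 2 and 3). The de-escalation levels are 3 mg BID continuously (Level -1) and 3 mg BID three weeks on, one week off (Level -1INT).

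- **Section 4.2, Level 1.** Step 1b: "If 1 of the first 3 evaluable subjects in Dose Level 1 exhibit a DLT in Cycle 1, then Dose Level 1 will be expanded". Step 1c: "If 0 of the first 3 evaluable subjects in Dose Level 1 exhibit a DLT in Cycle 1, then the dose of mirdametinib" goes up to Level 2. Step 2c, for two or more DLTs in three or in six: "then the mirdametinib dose will be de-escalated (see #3 below"), which is Level -1.
- **Section 4.2, Level 2.** Step 5b: "If ≤ 1 of the first 3 evaluable subjects in Dose Level 2 exhibit a DLT in Cycle 1, then a sufficient number" of subjects is added to reach six. Step 5c escalates to Level 3 if at most one of the six has a DLT. Step 5d: if two or more of the first three, or two or more "of the 6 evaluable subjects in Dose Level 2 exhibit a DLT in Cycle 1, then" 4 mg BID is declared the RP2D.
- **Section 4.2, Level 3.** Step 6d declares 6 mg BID the RP2D on the same counts.
- **Section 4.2, introduction to the levels.** De-escalation levels are used at the investigator's discretion "after the higher dose of mirdametinib is not tolerated"; it does not say which higher dose.
- **Section 10.1.** "Pending DLTs in dose levels 1-3, this arm will proceed to dose level -1 using mirdametinib as monotherapy". It gives no DLT count and no other destination.
- **Section 14.1, Arm 2.** If at most one of the first three "evaluable subjects in Dose Level 1 exhibit a DLT in Cycle 1, then Dose Level 1 will be expanded". The next sentence sends zero of three to escalation. Levels 2 and 3 are covered only by a reference back to these rules.
- **Stated operating figures.** The 14.1 table gives escalation probabilities of 0.9, 0.7, 0.5, 0.3 and 0.2 at true DLT risks 0.1 to 0.5. Sections 14.1 and 14.5 state a maximum of 18 evaluable patients, and 14.5 a minimum of 6.

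**The concern.** A 3+3 design is defined by its decision rules. If two current sections lead from the same observations to different next steps, the design is not fully specified and its operating characteristics cannot be stated. The Arm 2 RP2D is the dose carried into up to two expansion cohorts. Under 14.1 it also decides which Part 1 patients are pooled into the Efficacy Population. The escalation table is the only quantitative description of the dose finding, so it should match the rules at every level where escalation is possible. Arm 1 is never escalated, so the table can refer only to Arm 2, that is, to the steps from Level 1 to 2 and from Level 2 to 3.

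**Working it through.** Let p be the true DLT risk at a level and q = 1 − p.

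**Step 1: reproduce the 14.1 table.** If zero of three escalates at once, and one of three expands to six with escalation at one of six:

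P(escalate) = q³ + 3pq²·q³ = q³ + 3pq⁵.

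At p = 0.2: 0.512 + 0.6 × 0.32768 = 0.709.

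**Step 2: the Level 2 rule in 4.2.** If zero or one of three always expands to six:

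P(escalate) = P(at most 1 of 6) = q⁶ + 6pq⁵.

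At p = 0.2: 0.262 + 1.2 × 0.32768 = 0.655.

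| True risk | Table in 14.1 | Level 1 rule | Level 2 rule |
|---|---|---|---|
| 0.1 | 0.9 | 0.906 | 0.886 |
| 0.2 | 0.7 | 0.709 | 0.655 |
| 0.3 | 0.5 | 0.494 | 0.420 |
| 0.4 | 0.3 | 0.309 | 0.233 |
| 0.5 | 0.2 | 0.172 | 0.109 |

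The Level 1 rule rounds to the table in every row. The Level 2 rule rounds to 0.9, 0.7, 0.4, 0.2 and 0.1, so it misses at risks 0.3, 0.4 and 0.5.

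**Step 3: the overlap in 14.1 at zero of three.** The two branches reach opposite Level 1 decisions only if zero of three is followed by at least two DLTs in the next three:

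q³ × P(at least 2 of 3).

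- p = 0.1: 0.729 × 0.028 = 0.020
- p = 0.2: 0.512 × 0.104 = 0.053
- p = 0.3: 0.343 × 0.216 = 0.074

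These are also the differences between the last two columns above.

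**Step 4: 4.2 against 10.1.** Section 10.1 has no counts, so the 4.2 threshold of two or more DLTs is used for both.

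| Two or more DLTs at | Section 4.2 | Section 10.1, read literally |
|---|---|---|
| Level 1 (4 mg) | go to Level -1 | go to Level -1 |
| Level 2 (6 mg) | 4 mg BID is the RP2D | go to Level -1 |
| Level 3 (8 mg) | 6 mg BID is the RP2D | go to Level -1 |

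**Step 5: patient numbers.** Under 4.2 the shortest path is 3 at Level 1 and 3 at Level 2 = 6. The longest is 6 + 6 + 6 = 18, either upward or through Levels 1, -1 and -1INT. This is the stated range of 6 to 18. Under literal 10.1, failure at Level 3 can be followed by six at Level -1 and six at Level -1INT: 5 × 6 = 30. The shortest path is 9, for example 3 + 3 + 3 through Levels 1, -1 and -1INT.

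**Step 6: how often 4.2 ends where 10.1 has no branch.** The documents give no DLT rates by dose, so three sets are assumed for 4, 6 and 8 mg. Let A be the Level 1 pass probability (Step 1 formula), and B and C those at Levels 2 and 3 (Step 2 formula). Then P(RP2D is 4 mg) = A(1 − B) and P(RP2D is 6 mg) = AB(1 − C).

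| Assumed risks at 4/6/8 mg | 4 mg | 6 mg | Sum |
|---|---|---|---|
| 5/10/15% | 0.111 | 0.193 | 0.30 |
| 10/20/30% | 0.312 | 0.344 | 0.66 |
| 20/35/50% | 0.483 | 0.201 | 0.68 |

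For the middle row: 0.906 × (1 − 0.655) = 0.312, and 0.906 × 0.655 × (1 − 0.420) = 0.344.

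**The case against.** The best defence is that 4.2 is the only complete Arm 2 algorithm, with numbered steps, counts and a named RP2D for each outcome. Section 10.1 follows a list of dose levels, calls the design a standard 3+3 and gives no counts, so it can be read as a loose summary saying that de-escalation levels exist if needed. The stated range of 6 to 18 fits 4.2 and not literal 10.1. Much of this stands. A reader might infer that all three sections prescribe different actions for the same DLT counts; the documents do not support that, because 10.1 has no counts. What remains is that 10.1 names Levels 1 to 3 and a single destination, and that nothing in the text says 4.2 governs for Arm 2.

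On 14.1, the zero-of-three sentence is more specific than the one before it, step 1b of 4.2 expands on exactly one DLT, and the table fits immediate escalation. That makes the overlap easy to interpret, though not resolved. A reader might also take the chance of seeing zero of three (q³: 73%, 51% and 34% at risks of 10%, 20% and 30%) as the size of this problem. It is only how often the overlap arises; expansion after zero of three still ends in escalation unless two or more of the next three have DLTs.

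Step 1c of 4.2 points to step 4, which is Level -1INT, while Level 2 is step 5. A reader might infer that escalation could be misdirected to a de-escalation level. Step 1c itself names Level 2 and 6 mg BID, so this is a clerical slip.

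Finally, the 14.1 table is arithmetically correct for the rule it describes.

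**Conclusion.** The Arm 2 rules are inconsistent in three places of unequal weight.

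1. **Sections 4.2 and 10.1 after failure at Level 2 or 3.** This is the one that matters for the RP2D. The contradiction lies in the wording and needs no assumed rates. Its frequency does: about 0.30 to 0.68 in the three assumed scenarios, which are illustrations and not estimates.
2. **The overlap in 14.1 at zero of three.** Real, with a small effect on the Level 1 decision: about 2%, 5% and 7% of trials at risks of 10%, 20% and 30%.
3. **Two escalation rules within 4.2, one table in 14.1.** The table overstates the Level 2 escalation probability under 4.2: 0.5 against 0.42 at risk 0.3, 0.3 against 0.23 at 0.4, and 0.2 against 0.11 at 0.5.

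All probabilities assume independent DLTs with a constant risk at each level. No view is taken on which dosing rule is right.

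**What to change.** Put one complete Arm 2 decision table in a single section, with one action for each level and DLT count, and have the other two sections cite it without restating the rules. In doing so:

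- reconcile 10.1 with steps 5d and 6d of 4.2;
- remove the overlap in 14.1 between the at-most-one and zero branches;
- say whether the zero-of-three rule is meant to differ between Level 1 and Level 2;
- state the escalation probabilities for the rule kept, by level if the rules differ. If immediate escalation after zero of three is kept at both levels, the present table can stay as it is;
- confirm the range of evaluable patients for the rule kept;
- correct the step number in 1c as a clerical item.

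The sponsor decides which rule applies. The cost is protocol wording and at most one recalculated table.
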